3.1. The Purpose of Clinical Trial

The purposes of the clinical trial is aiming at validating the safety and efficacy of completely degradable occluder system and occluder surgical intervention delivery devices manufactured by Shanghai Shape Memory Alloy Co., Ltd.

3.2. Content

The trial is “The clinical trial for safety and efficacy in clinical application of completely degradable ventricular septal defect occlusion system”, as a perspective, multiple-centered, randomized control non-inferiority clinical trial with the 6 month occlusion successful rate of completely degradable occluder after occlusion as the primary evaluation indices, and with the ventricular septal defect occluder and the occluder intervention delivery devices manufactured by the company as the control. It is

estimated that there are 108 cases (54 pairs) of subjects included in the 4 central groups nationwide between December, 2018 and December, 2019, during the treatment courses, it is randomly applied the completely degradable occluder system and occluder surgical intervention delivery devices manufactured by Shanghai Shape Memory Alloy Co., Ltd or ventricular septal defect occluder and occluder intervention delivery devices already marketed, and carry out clinical follow up instantly after operation, one month after operation, three months after operation, and six months after operation. After completion of 6 months clinical follow up, it is carried out clinical summarization, used in the registered application for products.

4. The Background Materials for Clinical Trial

4.1. Background Information

Ventricular Septal Defect (VSD) is one of the common congenital cardiac diseases, covering about 20% of all congenital cardiac diseases. In 2002, Amplatzer invented the Eccentric perimembrane ventricular septal defect occluder, and carried out clinical application in multiple countries of Europe, US and Asian, etc. Among them, the number of application in China is the maximum. Among the statistical early stage clinical trial cases with Complications of atrioventricular block unexpected occurred during early stage and follow up period after surgery, the ratio of cases in need of implanting artificial heart pacemaker reached 3.8%, even with the incidence about 4 years after operation. Since the peripheral VSD occluder with nickel-titanium membrane has shown the unexpected severe complication in clinical trial, in particular with the higher incidence of complete atrioventricular block, FDA in US has not yet ratified the clinical application for this model of occluder in US. Targeting at the insufficiency in the current occluder in application, Shanghai Shape Memory Alloy Co., Ltd autonomously developed the completely degradable occluder with Independent intellectual property rights, with the following characteristics:

- 1、 The raw materials of occluder are completely degradable, after complete endothelialization in the defect location after implanting, the occluder is gradually degraded without toxicity in the degraded products, capable of complete

- disintegration and absorption by human body, without adverse reaction and long term latent risks;
- 2、 It is avoided of the conduction block existed in NiTi alloy occluder; as well as the long term mechanical friction resulted in the injury to the peripheral tissues, even in aortic perforation, and valve damages;
 - 3、 It should be avoided of the fracture in the NiTi thread of occluder resulting in the injury and the puncture of the myocardial tissues, endocarditis, hydropericardium, and hemopericardium, fistula formation, and pericardial tamponade, etc;
 - 4、 Without Ni ion separation out caused by bioelectricity or body fluids, and blood corrosion, resulting in the Ni ion toxicity in patients, as well as the allergy in minority of patients to Ni ion and other issues;
 - 5、 Without potential risks caused by non-degradability of NiTi occluder in long term, such as the patients are in need of atrial septum or ventricular septum paracentesis, where there is a NiTi occluder formerly implanted. The degradable occluder can be completely degraded after implanting for 3 years, without residue, and the defect position is replaced by nascent myocardial tissue, which could be punctured after several years.

The completely degradable ventricular septal defect occluder is woven by poly p-dioxanone (PDO) thread, with formation, within the scaffolding framework, it is stitched with PLA Polylactic acid membrane, and the stitching thread is PDO wire.

PDO is a kind of aliphatic polyester with excellent biocompatibility, bioabsorbability, and biodegradability. In its molecular chain, there is unique ether bonds, endowed it with excellent flexibility, suitable to be processed into thread materials, which is advantageous for weaving. As the absorbable suturing thread, the degradation of PDO is started from about 6 months, and basically degraded at 12 months, first, it is hydrolyzed from high molecular into large molecular, and then gradually degraded into small molecular, which are engulfed by cells into tricarboxylic acid cycle, and turned into acetone, finally degraded into carbon dioxide and water. As the absorbable suture wire, PDO has been approved by FDA in US long since 2004 (US J&J as absorbable suture), and in 2011, Chinese Tianjing Hensheng absorbable suturing

thread has also gained the approval by CFDA in China, and widely applied in various operations in general surgery, orthopedics, gynaecology, urology, hepatological surgery, etc, as well as the suturing and ligation of organs, subcutaneous tissues, and muscles. Since 2015, absorbable intraocular micro tube plug made from PDO pipe materials has been approved by FDA in US, to use in the treatment of eye dryness. Since 2011, blood vessel hemostatic clips made from PDO materials have been applied in the ligation closure for blood vessels in laparoscopic operation (Hangzhou Shenshi Science and Technology, absorbable blood vessel clips, as shown in Figure 2). Practice demonstrate, the materials are excellent in biocompatibility, without rejection, without complications.

Poly(lactic acid) (PLA) is amorphous polymer, with glass transition temperature between 50 and 60°C. Poly(lactic acid) degradation is divided into two steps, first, it is hydrolysis, PLA under the effects of body fluids (water), the copolymer bonds break, and the mechanical strength of materials reduce, and then the long chains are changed into short chains, until it is degraded into small molecular lactic acid monopolymer. And then it is enzymolysis, with small molecular lactic acid participated in the Tricarboxylic acid metabolism, and then generate into carbon dioxide and water, and discharge out of the body through the respiration and excretory system. The materials can be used as the medical surgery anti-sticking mucosal membrane, micro gel capsule for injection, micro bead and embedding agents, etc as the adjuvant of controlled release formulations, at the same time it can be used as porous brackets and skeletal fixation or tissue repairing materials for tissue engineering cell cultivation such as: Surgical operation suture thread, implanting pieces and artificial skin, artificial blood vessel, retina in ophthalmology, etc, after approval by FDA. The finished medical products with poly(lactic acid) as the raw materials include, Bio-fix company in Finland, Grand fix absorbable bone pegs and suturing thread in Japan, Johnson suturing thread in US, and SurgiWrap degradable anti-sticking mucosal membrane in US, etc.

4.2. Preclinical Trial Research Conditions

We have passed through the in vitro experiments and animal experiments, to carry out assessment for the biological safety, compatibility, and feasibility as well as efficacy of the degradable occluder.

In order to put the degradable occlusion system into clinical application as promptly as possible, and benefit the broad congenital heart diseases patients, it is now applied for the human body clinical trial research for the clinical validation of the efficacy and safety of new products, to gain the approval for the registration certificate of the products and marketing approval.

The current trial selected ventricular septal defect occluder and occluder intervention delivery devices manufactured by Shanghai Shape Memory Alloy Co., Ltd (refer to as Shanghai Shape in the following) as the clinical trial control products.

The model and specification already approved for marketing of ventricular septal defect occluder are as following: SQFDQ-IIi 04、SQFDQ-IIi 05、SQFDQ-IIi 06、SQFDQ-IIi 07、SQFDQ-IIi 08、SQFDQ-IIi 09、SQFDQ-IIi 10、SQFDQ-IIi 12、SQFDQ-IIi 14、SQFDQ-IIi 16.

The occluder intervention delivery devices model and specifications already approved for marketing are as following:

Models	Specifications
Type I	5F、6F、7F、8F、9F、10F、12F、14F
Type II	5F、6F、7F、8F、9F、10F、12F、14F
Type III	5F、6F、7F、8F、9F、10F、12F、14F
Type IV	5F、6F、7F、8F、9F、10F、12F、14F

Completely degradable occluder system and occluder surgical intervention delivery devices have been registered for inspection in the testing institutions recognized by SFDA and Quality Technological Monitoring Department of the State Council, with the testing results as eligible. Completely degradable occluder system registration inspection reports: SFDA Jinan Medical Instrument Quality Monitoring Inspection Center Inspection Report, with serial number as: Y2015092510;

The occluder surgical intervention delivery devices registration inspection report: Z-Y-0437-2018

The completely degradable occluder system and occluder surgical intervention delivery devices manufactured by the company have met all the conditions required by the current clinical trial research, with less expected adverse reaction for the products at present, however it cannot be obliterated of the possibility for adverse reaction during application of the

products.

5. Product Characteristics, Structural Compositions, Working Principles, Operating Mechanism, Model and Specification and Trial Scope

5.1. Product characteristics

The completely degradable ventricular septal defect occluder is woven by poly p-dioxanone (PDO) thread, with formation, within the scaffolding framework, it is stitched with PLA Polylactic acid membrane, and the stitching thread is PDO wire, both of which are completely degradable materials. Through specific processing technique, to ensure the occluder degradation is in match with the endothelialization, according to the animal experiment results:

- At one month, occluder products woven by PDO thread materials are started for endothelialization, and the HE staining demonstrated PDO thread materials have almost no changes;
- At three month, occluder products woven by PDO thread materials are finished for endothelialization, and the HE staining demonstrated PDO thread materials have basically no changes;
- At 6 months, HE staining demonstrated PDO thread materials started degradation;
- At 9 months, PDO thread materials are further degraded;
- At 12 months, PDO thread are mostly degraded, and left with the hollow cavity;
- At 24 months, the hollow cavity left by PDO thread degradation have gradually been filled with the growth of myocardial tissues;
- At 36 months, the hollow cavity after degradation have been completely filled by myocardial tissues.

5.2. Product Structure Composition, Working Principles, Operating Mechanisms

The completely degradable occluder system includes the degradable occluder, loader, delivery devices and safety rope.

Completely degradable occluder is woven by PDO (sealed with polyactic acid choke flow membrane), demonstrated as stretched stripes after pulling by strength, after the removal of which, it can automatically restore to over 80% of the formation shape. After regulation by safety rope, it can restore to original shape. Such performance ensures that the occluder can

firmly fix on the defect positions after it is in place. The performance of formation of stripe shape after pulling can pass the occluder through the occluder surgical intervention delivery devices into cardiac defect positions. The polyactic acid membrane in the occluder plays the role to choke the blood flow, after the implanting of occluder, it shall completely close the defects, to realize the purposes of healing the atrial septal defects.

The type of degradable occluder is thread materials woven type. The shape design is shown in Figure 1.

[figure not shown]

Figure 1. Type IIIIIIIVV diagrams of completely degradable occluder

H—The total height of the occluder A—The diameter of upper disc B—The diameter of lower disc C—Waist Diameter

Among them the type of loading devices is catheter type. The shape design is shown in Figure 2.

[figure not shown]

Figure 2. Loader Diagram

1. Loader sheath 2. Loader connector L is the length of loader

Among them the type of delivery devices is of clamp type. The shape design is shown in

Figure 3.

[figure not shown]
[figure not shown]

[figure not shown]
Figure 4. The complete design diagram of completely degradable occluder system

The occluder surgical intervention delivery devices are consisted of outer sheath, expander, loader, delivery device, guiding wire, and two way valve.

[figure not shown]
1. Outer sheath 2. Expander

Figure 5. Outer sheath and expander outfit

[figure not shown]
1. Outer sheath 2. Loader 3. Delivery Device

Figure 6. Outer sheath, loader and delivery device outfit

[figure not shown]
1. Loader sheath 2. Loader Connector

Figure 7. Loader Structure Diagram

[figure not shown]
1. Outer sheath 2. Standard luer taper 3. Extension Tube 4. Hemostatic Valve Connector

Figure 8. Outer Sheath Structure Diagram

1. Expanding tube 2. Expander connector (the inner hole is standard luer taper).

Figure 9. Expanding Tube Structure Diagram

1. Delivery rod 2. Fixing Screw 3. Rotational Handle

Figure 10. Delivery Rod Structure Diagram

5.3. Test Scopes

The test scopes of completely degradable occluder system: The current product is applied in the treatment of ventricular septal defect in congenital cardiac diseases;

The occluder surgical intervention delivery devices are dedicated in the surgical intervention operation, and they are used in the delivery of various occluders manufactured by the company into the lesion location for release. It is applied in the occlusion treatment for the atrial septal defects, ventricular septal defects and patent ductus arteriosus.

6. Products Indications and Contraindications, and matters in need of attention.

Indications:

Completely degradable ventricular septal defect occluder is a type of percutaneous ventricular

septal defects closure devices through catheter, used in the ventricular septal defects with abnormality of hemodynamics or enlargement of left ventricular inner diameter.

Contraindications:

- 1). Patients with moderate to severe resistant type pulmonary arterial hypertension.
- 2). There exists thrombus in the cardiac cavity. There is hemorrhagic diseases, such as active ulceration.

Matters in need of Attentions:

- 1). The degradable occluder system and occluder surgical intervention delivery devices have already been sterilized before discharge.
- 2). The product is disposable product, forbidden for application after resterilization after opening.
- 3). If it is discovered of the opening, damages, leakage of packages or over the sterilization validity period, please do not use it.
- 4). The selection of occluder delivery sheath is crucial, such defects as unmatched between the sheath tube and the occluder, may result in the delivery and withdrawal difficulty, even result in the blood vessel injury.
- 5). The product is only limited to the application by the physician already receiving occlusion technique trainings.
- 6). It is necessary to prepare for the emergency conditions, and withdraw the thrombus devices that may severely influence the flowing property of blood.
- 7). For allergic patients with polyactic acid, and poly (p-dioxanone), they may have allergic reaction for the product.
- 8). The product is applicable for MRI.
- 9). In order to avoid the adverse outcome, please read the manual carefully before application, in particular, it must take heed of all precautions and matters in need of attention.

7. General Design

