7.1.5.2. Exclusion Criteria

If there is any of the following condition, the current subjects should be excluded from the participation in the clinical trial:

- (1) Irreversible pulmonary blood vessel diseases; Severe pulmonary artery hypertension accompanied by shunts in double directions;
- (2) Hemorrhagic diseases or blood coagulation dysfunction already known (including thrombocytopenia resulted from heparin), with contraindications against platelet treatment, or possible of rejection for blood transfusion;
- (3) Septicemia or severe infections within one month before occlusion operation;
- (4) There exists thrombus in the location of occluder, and patients with venous thrombosis at the insertion point of the catheter;
- (5) Cardiac deformity patients survived with VSD;
- (6) Patients deemed by the researcher as inappropriate for the application of the current

product

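### The contraindications and indication in section 6 do not match the eligibility criteria in 7.1.5.1 and 7.1.5.2, so a patient contraindicated under section 6 can meet every explicit entry criterion

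*Combined protocol and SAP*

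**What the plan says.** Section 6 lists three contraindications to the degradable occluder. The first is "Patients with moderate to severe resistant type pulmonary arterial hypertension". The second and third share one item: "There exists thrombus in the cardiac cavity" and "There is hemorrhagic diseases, such as active ulceration". The indication in the same section is for a device "used in the ventricular septal defects with abnormality of hemodynamics or enlargement of left ventricular inner diameter". Section 5.3, immediately before it, gives the test scope as treatment of congenital ventricular septal defect, with no haemodynamic or ventricular-size condition.

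The exclusion criteria in 7.1.5.2 deal with the same subjects in other terms. Exclusion 1 has two limbs: irreversible pulmonary vascular disease, and "Severe pulmonary artery hypertension accompanied by shunts in double directions". Exclusion 2 covers known haemorrhagic disease or coagulation dysfunction. Exclusion 4 reads "There exists thrombus in the location of occluder, and patients with venous thrombosis at the insertion point of the catheter". Exclusion 6 leaves out anyone the investigator considers unsuitable for the product.

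The four inclusion criteria in 7.1.5.1 concern consent and follow-up; age, weight and pregnancy; an effective shunt opening of 3 to 14 mm; and the distance from, and state of, the aortic valve.

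**The concern.** A protocol should not say in one section that a device is contraindicated in a patient whom another section lets through on every written criterion. The first issue is patient safety. Subjects may be as young as one year (7.1.5.1), and the implantation in 7.3.2 is an open-chest procedure through the right ventricle.

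The second issue is the meaning of the result. Section 3.2 says the trial is to support product registration. If the indication in section 6 is narrower than the population enrolled, the data describe a different group from the one the indication names.

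The third is the analysis sets. If a contraindicated patient breaches no listed criterion, the per-protocol definition gives no explicit ground for removing that patient.

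**Working it through.** No figure in the plan is at issue, and the sample size of 54 per group does not depend on this point. The check sets section 6 beside the entry criteria and then asks which text controls entry and analysis.

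| Item in section 6 | Nearest eligibility text | Covered? |
|---|---|---|
| Thrombus in the cardiac cavity | Exclusion 4: occluder location; venous thrombosis at the insertion point | In part. Intracardiac thrombus away from the occluder site meets no listed exclusion |
| Moderate to severe resistant-type pulmonary arterial hypertension | Exclusion 1: irreversible pulmonary vascular disease; severe hypertension with bidirectional shunt | Depends on an undefined term (see below) |
| Haemorrhagic disease | Exclusion 2: known haemorrhagic disease or coagulation dysfunction | Yes |
| Indication: abnormal haemodynamics or left ventricular enlargement | Inclusion 1 to 4: no such requirement | No; section 5.3 does not require it either |

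**Pulmonary hypertension.** The second limb of exclusion 1 needs both a severe grade and a bidirectional shunt, so it does not reach moderate disease, or severe disease without that shunt. The first limb has no grade but needs irreversibility. There are two readings:

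- If resistant type always means irreversible, the first limb covers the whole contraindication and there is no gap.
- If it does not, moderate resistant-type disease that is not irreversible is contraindicated but not excluded. So is severe resistant-type disease that is neither irreversible nor accompanied by a bidirectional shunt.

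The protocol defines neither term, so the text does not settle which reading applies.

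**Thrombus.** No definition is needed here. The cardiac cavity is a wider place than the position of the occluder.

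**Indication.** This gap lies in the inclusion criteria, not the exclusions. It is also a difference between sections 5.3 and 6.

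**Which text controls entry and analysis:**

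- 7.1.3, item 2: the investigator goes to the central randomisation system once the inclusion criteria are met.
- 7.1.5.4: the subject proceeds if the inclusion criteria are satisfied and no exclusion applies.
- 7.4, item 1: the monitor confirms subjects against the inclusion criteria.
- 8.9: the full analysis set is those randomised in whom a device was used. The per-protocol set removes severe breaches, illustrated by failing the inclusion criteria or meeting an exclusion criterion.

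None of these refers to section 6. A patient with, for example, intracardiac thrombus away from the occluder site could satisfy every explicit criterion, be randomised and implanted, and stay in both the FAS and the PPS, on which 8.9 bases the primary analysis.

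**The case against.** The strongest reply is that investigators would not ignore section 6. Exclusion 6 removes patients unsuitable for the product, and a patient whom the same protocol calls contraindicated fits that description. Section 7.1.3 requires strict adherence to the protocol, section 7.3.3 tells users to heed all precautions, and section 10.2 names misunderstanding of indications and contraindications as a cause of failure. Monitoring item 4 in 7.4 checks protocol compliance in general, and the examples of a severe breach in 8.9 are open-ended. All this makes enrolment of such a patient less likely. It does not make exclusion explicit: exclusion 6 rests on judgement and does not cite section 6, and the other passages are general instructions rather than screening checks.

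The second reply is that the pulmonary hypertension mismatch may be only a matter of translation. That stands as a possibility, and this part of the point is conditional on it. The thrombus and indication differences do not depend on it.

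The third is that the inclusion criteria agree with section 5.3. They do, but then 5.3 and 6 disagree with each other, and that still has to be resolved.

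A reader might go further and infer that material allergy is another unexcluded contraindication. The documents do not support that. Section 6 places the polymer allergy among its precautions ("For allergic patients with polyactic acid, and poly (p-dioxanone), they may have allergic reaction for the product"), not its contraindications. Nickel allergy appears only in the background account of older occluders in 4.1 ("as well as the allergy in minority of patients to Ni ion and other issues"). Section 6 concerns the degradable device, and the control device's own contraindications are not in the documents. The absence of an allergy exclusion therefore contradicts nothing.

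**Conclusion.** The point holds as an internal inconsistency. Of the three contraindications in section 6, haemorrhagic disease is covered, intracardiac thrombus is covered only in part, and pulmonary hypertension is fully covered only if resistant type always means irreversible. The indication is not carried into the inclusion criteria and is narrower than section 5.3.

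The consequence is a possibility, not a prediction. A patient contraindicated under section 6 could meet every explicit criterion and remain in both primary analysis sets. The number of such patients cannot be derived from the documents.

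A reader might also infer that a few of these patients could tip the non-inferiority result. The documents do not support that either. The primary endpoint in 7.1.6 is residual shunt at six months, nothing in the text links these conditions to residual shunt, and randomisation could place such patients in either arm. The case rests on patient safety and a clear definition of the study population, not on a calculated bias.

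**What to change.** Go through sections 5.3, 6, 7.1.5.1 and 7.1.5.2 line by line so that each contraindication and the indication read the same wherever they appear. Define resistant type and irreversible, or use one term throughout. Put each agreed item on the screening checklist, so that the randomisation step, the monitor's check and the per-protocol definition all pick it up through the listed criteria. Which wording is clinically right is for the sponsor and investigators to decide.

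The cost is a wording amendment and a few checklist items. Recruitment may be slightly slower if the reconciled criteria turn out stricter than the present ones. An echocardiogram is already scheduled at screening in 7.2; whether it is enough for each item is for the investigators to judge.
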